9.1 STATISTICAL HYPOTHESIS

In terms of concordance, i.e. the proportion of EM+optical imaging and histopathology test results that match, the null hypothesis is that concordance $\leq 80\%$, and that the expected concordance (or concordance worth detecting) is 90%. Based on a positivity prevalence of 80%, i.e. 80% true malignant and 20% true benign, an 80% concordance can produce a kappa value ranging from 0 to 0.55; and a 90% concordance can produce a kappa value ranging from 0.62 to 0.74. Based on these numbers, the null and alternative hypotheses for this study are set in terms of kappa as follows:

- $H_0: \text{kappa} \leq 0.4$
- $H_1: \text{kappa} > 0.4$

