2.4.2 Known Potential Benefits

Patients with focal hepatic lesions need biopsies for accurate diagnosis, and the ones with small focal hepatic lesions approximately $l < 3$ cm required more accurate methods to guide the biopsy needle into the lesion. Accurate diagnosis of HCC or cancer is important in these patients since these patients are usually candidates for focal ablation and subsequent liver transplantation. Optical molecular imaging has been reported as a promising method for better detection of the tumors. Our null hypothesis is that there is discordance greater than 20% between the fluorescence signal during biopsy and histopathology. We anticipate that with the combination of both optical molecular imaging guidance and electromagnetic guidance, we can address issues of tumor heterogeneity, by guiding intra-tumoral sampling towards the most viable and aggressive lesion components to improve the biopsy yield.

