9 STATISTICAL CONSIDERATIONS

Three medical procedures will be conducted to diagnose liver lesions as benign/malignant (negative/positive):

- (1) Histopathology, using well-established standard procedures.
- (2) ICG fluorescent signal at the in-vivo site of biopsy using a combination of OMI and EM tracking.
- (3) ICG fluorescent signal ex vivo of the specimen obtained using a combination of OMI and EM tracking.

For (2) and (3), malignancy determination will be based on TBR: $TBR \geq 2$ will produce a malignant diagnosis, and $TBR < 2$ will produce a benign diagnosis.

One main objective is to evaluate the agreement between (1) and (2), and between (1) and (3), with (1) considered as the gold standard. Since determinations are dichotomous, Cohen's kappa will be used to assess agreement.

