9.2 SAMPLE SIZE DETERMINATION

Based on the null kappa value $k_0=0.4$, a kappa value $k_1=0.7$ worth detecting, alpha (Type I error) equal to 0.05, 80% power, and a prevalence (true positive rate) of 80%, the resulting sample size from a one-sided test is 77.

Generally, $\kappa=0.4$ is considered as fair/moderate agreement, and $\kappa=0.7$ as substantial agreement.¹ With an 80% true positive rate, $\kappa=0.4$ corresponds to an 86% sensitivity and 55% specificity, and $\kappa=0.7$ corresponds to a 93% sensitivity and 80% specificity

With data on 77 cases, it is worthwhile determining the optimal cut-off point for TBR to confirm whether $TBR=2$ is optimal. This can be done based on Youden's index in receiver operating characteristic (ROC) analysis.

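### Sections 2.4.2 and 9.1 print a concordance null, but the test, alpha, power and N = 77 belong to kappa 0.4 vs 0.7; rejecting kappa ≤ 0.4 does not by itself show concordance above 80%

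*Combined protocol and SAP*

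**What the plan says.** Section 2.4.2 (Known Potential Benefits) has one sentence on the hypothesis: "Our null hypothesis is that there is discordance greater than 20% between the fluorescence signal during biopsy and histopathology". It does not mention kappa.

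Section 9 names histopathology (1), the in vivo signal (2) and the ex vivo signal (3), calls a lesion malignant at TBR ≥ 2, and chooses Cohen's kappa: "One main objective is to evaluate the agreement between (1) and (2), and between (1) and (3").

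Section 9.1 opens on the concordance scale: "In terms of concordance, i.e. the proportion of EM+optical imaging and histopathology test results that match, the null hypothesis is that concordance" is at most 80%, with 90% worth detecting. At 80% prevalence of malignancy it then gives the matching kappa values: "an 80% concordance can produce a kappa value ranging from 0 to 0.55", and 0.62 to 0.74 at 90% concordance. It then changes scale: "Based on these numbers, the null and alternative hypotheses for this study are set in terms of kappa as follows", followed by H0: kappa ≤ 0.4 and H1: kappa > 0.4.

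Section 9.2 takes one-sided alpha 0.05, 80% power and 80% prevalence for kappa 0.4 against 0.7; "the resulting sample size from a one-sided test is 77". It adds that kappa 0.4 "corresponds to an 86% sensitivity and 55% specificity" and that kappa 0.7 "corresponds to a 93% sensitivity and 80% specificity". No test, threshold, alpha or power is given for concordance.

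**The concern.** Two different statements are both called the null hypothesis. Only the kappa statement has a test and an error rate. A reader of 2.4.2 alone never learns that kappa is what is tested, and the wording of 9.1 suggests that kappa 0.4 stands in for 80% concordance.

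At stake is what the final report may say. If kappa ≤ 0.4 is rejected, the protocol text would let an author write that the stated null of concordance ≤ 80% was rejected. The same data may not refute that null, and the 5% error rate does not cover the claim.

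**Working it through.** **Inputs.** Prevalence 0.8, one-sided alpha 0.05, power 80%, kappa 0.4 and 0.7, N = 77, and the sensitivity/specificity pairs 86/55 and 93/80 (all from 9.1 and 9.2). The plan does not say which form of kappa test will be used, so two are shown. The *design* version uses a fixed critical value from the null variance (an assumption). The *Wald* version uses the variance estimated from the data (Fleiss-Cohen-Everitt).

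**1. The plan's N.** With both margins at 0.8, chance agreement is 0.8² + 0.2² = 0.68. The large-sample variance of kappa times n is 1.272 at kappa 0.4 and 0.817 at kappa 0.7. Then

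n = [(1.645·√1.272 + 0.842·√0.817) / 0.3]² ≈ 76.0, rounded up to 77.

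The plan's figure reproduces. The design critical value is 0.4 + 1.645·√(1.272/77) = 0.611.

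**2. The plan's kappa ranges.** For sensitivity Se and specificity Sp:

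- concordance po = 0.8·Se + 0.2·Sp
- device-positive rate q = 0.8·Se + 0.2·(1 − Sp)
- chance agreement pe = 0.8·q + 0.2·(1 − q)
- kappa = (po − pe)/(1 − pe)

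At 80% concordance:
- 100/0: q = 1, pe = 0.80, kappa = 0.
- 75/100: q = 0.60, pe = 0.56, kappa = 0.24/0.44 = 0.545.

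At 90% concordance:
- 100/50: kappa = 0.16/0.26 = 0.615.
- 87.5/100: kappa = 0.28/0.38 = 0.737.

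Both printed ranges are right.

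**3. Where the two nulls meet.** At 86/55, po = 0.798, pe = 0.6668 and kappa = 0.1312/0.3332 = 0.394, so the boundaries nearly coincide. On the 80% concordance line kappa equals 0.4 at about 86.1/55.6. At higher specificity a device can have 80% concordance and kappa above 0.4. It is then inside the concordance null and outside the kappa null.

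**4. Chance of rejecting kappa ≤ 0.4** (all 2×2 tables enumerated, n = 77, prevalence 0.8):

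| Sens/spec (%) | Concordance | Kappa | Design | Wald |
|---|---|---|---|---|
| 86/55 | 79.8% | 0.394 | 3.4% | 5.4% |
| 90/40 | 80% | 0.324 | 1.2% | 1.6% |
| 87.5/50 | 80% | 0.375 | 2.6% | 4.0% |
| 85/60 | 80% | 0.419 | 4.8% | 8.0% |
| 80/80 | 80% | 0.490 | 12% | 22% |
| 75/100 | 80% | 0.545 | 23% | 47% |

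On the 80% line the rate passes 5% at a specificity of about 61% (design) or 53% (Wald). Below that the kappa test is conservative for the concordance null.

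**5. Single data sets, assuming 62 malignant and 15 benign.**
- 53/62 and 13/15 correct: po = 66/77 = 0.857, pe = (62·55 + 15·22)/77² = 0.631, kappa = 0.613. Kappa ≤ 0.4 is rejected by both versions, yet the exact one-sided 95% lower bound for 66/77 is 77.5%.
- 60/62 and 8/15 correct: po = 68/77 = 0.883, pe = (62·67 + 15·10)/77² = 0.726, kappa = 0.574. Neither version rejects, yet the lower bound for 68/77 is 80.5%.

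The two conclusions can split in either direction.

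**6. What a concordance statement would need.** The bound is 79.0% at 67/77 and 80.5% at 68/77, so 68 matches are needed. P(X ≥ 68 | 77, 0.8) = 4.0% and P(X ≥ 68 | 77, 0.9) = 76%.

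**The case against.** The case for leaving the text alone is strong in several respects.

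- **The operative test is identifiable.** Section 9 names kappa, 9.1 moves to kappa openly with labelled hypotheses, and 9.2 attaches alpha, power and N to it. A statistician following section 9 would run one test, and it is valid. This stands. A reader might infer that the sample size or the test is wrong; neither is.
- **The large error rates lie away from the plan's assumptions.** At 86/55 the nulls practically agree. The 80/80 row pairs the specificity of the plan's alternative with a sensitivity the plan never states, and 75/100 is an extreme. The small pilot series in 2.3.5 had TBR above 2.0 in all target lesions, including a granulomatous one. That points to low specificity, where the kappa test is the stricter of the two. This also stands. A reader might infer that the trial carries a 23% to 47% type I error, but those rates concern a concordance claim at one extreme point, not the kappa test.
- **No passage says a kappa rejection will be reported as concordance above 80%.** True. But 2.4.2 offers no other null and 9.1 still uses that label, so the text invites the statement.
- **The word concordance is used differently in sections 3, 4.1 and 9.4.3.** A reader might conclude that the null in 9.1 is therefore undefined. It is not: 9.1 defines its own concordance as the share of matching results. Those other uses add nothing to this point.
- **Power.** A reader might think 9.2 promises 80% power for any device with 90% concordance. It ties power to kappa 0.7, so 9.2 needs no change.

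**Conclusion.** The inconsistency is real and limited to how the null is stated. Rejecting kappa ≤ 0.4 supports a conclusion about kappa with its stated error rate. It does not by itself support the statement that concordance exceeds 80%. The gap is negligible near the plan's null point (3.4%/5.4%), reverses at lower specificity, and becomes material if specificity is high and sensitivity low (12%/22% at 80/80).

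These figures assume 80% prevalence and 77 evaluable cases. The first of each pair also assumes the 0.611 critical value, because the plan does not specify the test statistic. That the two nulls differ needs none of these calculations: it follows from the kappa range printed in 9.1. Severity is minor to moderate.

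**What to change.** 1. **Section 2.4.2:** replace the discordance sentence with: *The formal null hypothesis is kappa ≤ 0.4 (section 9.1).*
2. **Section 9.1:** present 80% and 90% concordance as the motivation for the kappa values, not as a null, and add: *Rejecting H0 does not by itself show concordance above 80%. For each comparison (in vivo vs histopathology, ex vivo vs histopathology) the proportion of matching benign/malignant calls at TBR 2 will be reported with its exact one-sided 95% lower bound, and any statement that concordance exceeds 80% will rest on that bound, not on the kappa test.*

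With 77 evaluable cases the bound exceeds 80% at 68 or more matches; the cut-off must be recomputed for the actual evaluable number. This is a reporting condition beside the kappa result, not a second success criterion.

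**Cost:** wording in two sections and one exact bound per comparison. N, procedures and the kappa test do not change. The downside is that the concordance statement has 76% power at 90% concordance (type I error 4.0%). At the plan's target of 93/80, about 6.5% (design) or 10.0% (Wald) of trials would reject kappa ≤ 0.4 without supporting it.

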9.2 SAMPLE SIZE DETERMINATION

Based on the null kappa value $k_0=0.4$, a kappa value $k_1=0.7$ worth detecting, alpha (Type I error) equal to 0.05, 80% power, and a prevalence (true positive rate) of 80%, the resulting sample size from a one-sided test is 77.

Generally, $\kappa=0.4$ is considered as fair/moderate agreement, and $\kappa=0.7$ as substantial agreement.¹ With an 80% true positive rate, $\kappa=0.4$ corresponds to an 86% sensitivity and 55% specificity, and $\kappa=0.7$ corresponds to a 93% sensitivity and 80% specificity

With data on 77 cases, it is worthwhile determining the optimal cut-off point for TBR to confirm whether $TBR=2$ is optimal. This can be done based on Youden's index in receiver operating characteristic (ROC) analysis.

9.3 POPULATIONS FOR ANALYSES

The target study population is patients with focal hepatic lesions with imaging. Features are suspicious for hepatocellular carcinoma or other liver neoplasm. Patients whose imaging findings suggest liver cancer (hepatocellular carcinoma) or other metastatic liver cancer for whom image-guided percutaneous biopsy is planned.

Accurate diagnosis of HCC and other liver malignancies is important in these patients since these patients may be candidates for liver transplantation or bridging transarterial chemoembolization or palliative focal ablation with systemic chemotherapy. Eligible patients demonstrate a focal hepatic lesion for which percutaneous image-guided biopsy is planned. The subject selection based on the race, ethnicity, sex and age has been considered based on the reported statistics of the HCC population.

Recruitment of the participants will be through the referring clinicians at NIH. The accrual will extend to different race and ethnicities and both sex. Since the safety of EM methods and ICG is not reported in children, we will enroll participants > 18 years to avoid any possible adverse events in children

9.3.1 Evaluable for toxicity

The following adverse event management guidelines are intended to ensure the safety of each patient while on the study. The descriptions and grading scales found in the revised NCI Common Terminology Criteria for Adverse Events (CTCAE) version 4.0 will be utilized for AE reporting. All appropriate treatment areas should have access to a copy of the CTCAE version 4.0. A copy of the CTCAE version 4.0 can be downloaded from the CTEP web site (http://ctep.cancer.gov/protocolDevelopment/electronic_applications/ctc.htm#ctc_40).

Incidence of 1% to 10%: diaphoresis, headache, pruritus, skin discoloration at the intravenous site. In subjects allergic to iodine, anaphylaxis reactions have occurred. The total dose administered will not exceed 40 mg per day. Of note, doses of up to 5 mg/kg have been administered as routine in Japan without adverse reactions. All adverse events experienced by participants will be collected from the time ICG is administered, through the study, and until the patient is off treatment.

9.3.2 Evaluable for objective response

The metric to evaluate where ICG localizes is TBRs and will be calculated by dividing the mean fluorescence intensity within the lesion by the mean fluorescence intensity within the adjacent

¹ Landis, J.R. & Koch, G.G. (1977). "The measurement of observer agreement for categorical data". *Biometrics*, 33 (1): 159–174.

liver parenchyma with in vivo and ex vivo samples. All specimens will be sent to NCI Laboratory of Pathology for diagnosis and research as defined by the patient's primary protocol.

9.3.3 Evaluable Non-Target Disease Response

The intervention (guided biopsy) is performed at a single point, and will not alter disease burden. Thus, no patients will be classified as evaluable for non-target disease response.

9.4 STATISTICAL ANALYSES

9.4.1 General Approach

All patients who enroll in the study and complete the biopsy procedure will be evaluable for an objective response. Response is defined as localization of the target lesion and lends information regarding the feasibility of using the optical imaging device and EM tracking tool to guide liver biopsies. Fluorescence microscopy showing a clear delineation between malignant and normal tissue is also an objective response.

The main intervention of the study is the ability to improve biopsy guidance. Please note that standard pathology results of the hepatic biopsies will be part of routine clinical care and will be the responsibility of the NIH primary team to review and to provide appropriate follow up and clinical management. The tracking and fluorescence results will not be shared with participants, as these results are unlikely to have direct effect clinically on patient care. In addition to routine histological analysis, additional analysis for specific molecular markers will be performed in the NCI Laboratory of Pathology, as clinically indicated. However, all study-specific results are bench studies and will not be used in patient care decision making, thus we do not anticipate obtaining any incidental findings since the intervention is technical in nature regarding the biopsy procedure itself.

The main intervention of the study is the ability to improve biopsy guidance. Please note that standard pathology results of the hepatic biopsies will be part of routine clinical care and will be the responsibility of the NIH primary team to review and to provide appropriate follow up and clinical management. The tracking and fluorescence results will not be shared with participants, as these results are unlikely to have direct effect clinically on patient care. In addition to routine histological analysis, additional analysis for specific molecular markers will be performed in the NCI Laboratory Pathology, as clinically indicated. However, all study-specific results are bench studies and will not be used in patient care decision making, thus we do not anticipate obtaining any incidental findings since the intervention is technical in nature regarding the biopsy procedure itself.

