2.3.11 Software

The EM and optical display software components analyze the EM and optical data and signal outside of the body, and the information is not used to guide the needle placement or the biopsy sample. The commercial EM needle, described above, and the commercial EM field generator and its commercial advanced programming interface are analyzed by custom software in order to co-display the local optical signal as well as the EM tracking fusion biopsy location in relation to a pre-procedural CT or MRI image. This information will be analyzed post-procedure, but is not used for navigation of the device. This system and multiple commercial fusion biopsy platforms (UroNav & PercuNav, Philips, for example) have been in clinical use on IRB-approved protocols at NIH for 15 years. These NIH research studies are currently approved under an IDE exemption. The OMI/EM system in its entirety has been thoroughly tested in phantoms as well as live animals (woodchuck liver cancer tumors for biopsy). This *in vivo* testing, included the EM tracking / fusion display components, the OMI pediatric cystoscope-urethroscope, and the combined signal display. This custom software platform incorporates EM fusion co-display (that tracks, fuses, and displays the needle with respect to CT images). The system also combines this EM fusion co-display navigation with the software that adjusts the camera (optical signal) functions from the pediatric cystoscope-urethroscope, and co-displays the OMI camera feed (ICG dye) in real time. DICOM images are loaded onto workstation computer by network transfer directly from the DICOM server/client. The graphical user interface includes tri-planar reconstructed views (sagittal, coronal, and axial) next to the images. The coil sensor in the inner stylet guider needle tip gives position and orientation to reformat and display the corresponding CT display planes. The device location within the registered image is updated in real-time at 10 frames per second. Thus both EM and optical information provide position and ICG levels, respectively, in real time simultaneously. This information however, will NOT be used to guide the biopsy needle to a sample location for biopsy or data sampling. The optical and EM data will be analyzed after the procedure and do not impact the biopsy sampling location.

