We propose a trial to determine the feasibility of using optical molecular imaging (a low cost, real-time, high resolution imaging discipline) for minimally invasive liver biopsy guidance in patients with diagnosed or suspected HCC or metastatic CRC. Patients who require a clinically indicated or separately IRB approved research liver biopsy would after consent, have the OMI performed during biopsy but not as the primary directorate to the biopsy site. The standard of care imaging and cognitive registration would be employed for navigation or guidance of needle and OMI would act as a bystander. Nonetheless, data from OMI imaging would be obtained and evaluated with ex vivo POC OMI and histopathology. Correlations from these studies might support a future larger clinical trial, with different goals that might not exclude efficacy and safety, or even allow for guidance of the needle if separately IRB-approved.

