5.1 INCLUSION CRITERIA

In order to be eligible to participate in this study, an individual must meet all of the following criteria:

- Patients must have imaging findings consistent with hepatocellular carcinoma or other liver neoplasms or metastasis, for whom image-guided percutaneous biopsy is planned as clinically indicated or IRB-approved under a separate research protocol.
- Patients must have at least one lesion that can readily be biopsied per Principal Investigator.

- Age >18 years.
- Patients must have the ability to understand and the willingness to sign a written informed consent document.
- Evidence of post-menopausal status or negative urinary or serum pregnancy test for female pre-menopausal patients. Women will be considered post-menopausal if they verbally report amenorrhea for 12 months without an alternative medical cause, or have had surgery or received chemicals to induce menopause.

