5.5 SCREEN FAILURES

Recruitment for this protocol is by invitation only; as such referral to this protocol is dependent on the evaluation of the investigator of the primary protocol. Individuals who do not meet the criteria for participation in this study (screen failure) may be considered for rescreen at the discretion of the PI/ referral team. However, patients who have screened, found eligible, signed a consent, and assigned a unique study ID but become ineligible consequently for various reasons

prior to the biopsy, will be considered inevaluable. These patients will be considered a “screen failure” and his/ her unique study ID will be counted towards overall total accrual.

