6.1.2 In-procedure biopsy

Tumor biopsy is divided into several stages or parts, described below. The first step is the standard of care preparation of the site and imaging of the liver, infiltration of local anesthesia followed by placement of the PercuNav coaxial needle by ultrasound guidance and EM tracking and co-display into the liver parenchyma. The next step requires a very short pause to thread that pediatric scope inside the PercuNav sheath. This is done by removing the PercuNav inner stylet from the hollow sheath. Once the scope is in the sheath, it is advanced in order to allow for signal sampling from normal liver. After acquiring images from normal liver, the scope is removed and once again the PercuNav needle inner stylet is reinserted, and the needle is advanced and manipulated into the target lesion in the usual standard fashion with standard clinical image-guidance. When the target is reached, the same process ensues, with exchange of the inner stylet for the scope, and subsequent repeat ICG OMI imaging occurs again. Finally, the PercuNav stylet is removed and replaced with a standard spring-deployed biopsy needle, and tissue core biopsy sampling occurs. Except for the two pauses, the biopsy procedure occurs as per usual medical practice, with standard clinical image guidance determining the location of biopsy tissue sampling, as is standard practice for many decades at NIH and around the globe. Thus, in summary, in order to record the data (optical study has 2 steps).

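### The feasibility response in 9.4.1 does not depend on optical output, does not test the EM position, and leaves out uncompleted procedures, so it says little about whether the devices could be used

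*Combined protocol and SAP*

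**What the plan says.** **Response and its denominator.** Section 9.4.1 sets the denominator: "All patients who enroll in the study and complete the biopsy procedure will be evaluable for an objective response". It then gives the outcome: "Response is defined as localization of the target lesion and lends information regarding the feasibility of using the optical imaging device and EM tracking tool". The sentence ends by referring to guiding liver biopsies. It names no modality, reader or threshold. A second route follows: "Fluorescence microscopy showing a clear delineation between malignant and normal tissue is also an objective response".

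**Who reaches the lesion.** Section 4.2: "The standard of care imaging and cognitive registration would be employed for navigation or guidance of needle and OMI would act as a bystander". Section 6.1.2 describes the procedure as usual practice apart from two pauses, "with standard clinical image guidance determining the location of biopsy tissue sampling". Section 2.3.11: "The optical and EM data will be analyzed after the procedure and do not impact the biopsy sampling location". Section 5.1 adds: "Patients must have at least one lesion that can readily be biopsied per Principal Investigator".

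**Where device output is required.** Sections 4.1 and 9.4.3 list four items that must all be present: (1) diagnostic tissue, (2) imaging confirmation of the sampled region, (3) an ICG signal from the apparatus, (4) an EM fusion display of the biopsy location. Both sections call this concordance, and neither refers to the 9.4.1 response. Section 9.3.2, on evaluability for response, names the target-to-background ratio (TBR) as the metric for where ICG localizes. Sections 9 to 9.2 set the formal test, which is Cohen's kappa against histopathology. Section 9.4.2, on the primary endpoint analysis, contains only timing.

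**The concern.** In section 9.4, the 9.4.1 response is the only outcome expressly tied to feasibility of the two tools. Standard guidance takes the needle to the lesion and the device data do not alter the sampling site. Reaching the lesion is then mainly a result of standard care. A patient whose scope gave no usable image still counts as a response when the ordinary biopsy reached its target.

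The completer denominator works in the same direction. A procedure abandoned partway, for instance during a stylet and scope exchange, may be exactly the failure a feasibility study should count, yet it leaves the rate. What is at stake is whether the reported figure can answer the primary objective.

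**Working it through.** **1. The plan's own figure.** Inputs from 9.2: null kappa 0.4, alternative 0.7, one-sided alpha 0.05, power 80%, prevalence 80%. With the Fleiss-Cohen-Everitt variances and both marginals at 0.80, Q0 = 1.272 and Q1 = 0.817.

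n = [(z0.95·√Q0 + z0.80·√Q1)/(0.7 − 0.4)]² = [(1.6449 × 1.1278 + 0.8416 × 0.9040)/0.3]² = 76.03, rounded up to 77.

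The stated 77 reproduces, and nothing below changes it.

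**2. The response rule applied to single patients.**

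| Patient | 9.4.1, read literally | Device-based technical success |
|---|---|---|
| Lesion reached, both OMI readings usable, EM display agrees with imaging | Response | Success |
| Lesion reached, no usable OMI image, biopsy completed | Response | Failure |
| Lesion reached, EM display absent or at odds with imaging | Response | Failure |
| Procedure abandoned before completion | Not counted | Failure |

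A failed scope exchange therefore never lowers the 9.4.1 rate. If the biopsy goes on and reaches the lesion, the patient is a responder. If it stops, the patient leaves the denominator.

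**3. Size of the insensitivity.** Let L be the chance that standard guidance localizes the lesion and s the chance that the devices give usable output. Both are assumed, and taken as independent. The literal rate is L. A rate that also requires device output is L × s. Expected counts of 77:

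| L | 9.4.1 response, any s | s = 0 | s = 0.5 | s = 0.8 | s = 1 |
|---|---|---|---|---|---|
| 0.55 | 42 | 0 | 21 | 34 | 42 |
| 0.80 | 62 | 0 | 31 | 49 | 62 |
| 0.95 | 73 | 0 | 37 | 59 | 73 |

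The lowest L is an extreme reading of 4.2, which cites up to 45% of small lesions as poorly seen with the needle in place (1 − 0.45 = 0.55). Poor visibility is not the same as failed localization. The level of the literal rate depends on L, but in every row it is the same for all s.

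**4. Denominator.** Suppose f of 77 started procedures are abandoned and the rest localize. The completer rate is 100% for any f. Over all started it is (77 − f)/77:

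- f = 2: 75/77 = 97.4%
- f = 5: 72/77 = 93.5%
- f = 8: 69/77 = 89.6% (exact 95% CI 80.6 to 95.4), against 69/69 = 100% (94.8 to 100)

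The documents give no value for f.

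**5. The TBR reading.** If localization means ICG localizing to the lesion, and the plan's cut-off of 2 is applied (9.4.1 does not say so), then at 80% prevalence a perfectly accurate device scores 0.80 × 77 = 61.6 responders. A device that always reads 2 or more scores 77. A technically sound low reading in a benign lesion would count as a non-response, so this is not a measure of technical feasibility either.

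**6. Can kappa stand in?** It does depend on the devices. With an uninformative TBR (kappa 0, 80% called positive), the test rejected in 0 of 200,000 simulated trials. The rejection boundary is 0.4 + 1.6449 × √(1.272/77) ≈ 0.61. But kappa measures agreement with pathology among patients who have both results. A patient without a usable reading has no TBR category to pair, so kappa does not measure how often the devices could be used.

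**The case against.** **The plan as a whole is not blind to the devices.** This stands. Section 4.1 puts the four-item check beside its statement of the primary endpoint, and items 3 and 4 fail if the devices give nothing. But that check is called concordance, and no text makes it the 9.4.1 response or the feasibility result.

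**Localization may mean localization with the tools, or of ICG.** The end of the sentence and 9.3.2 make this possible. It shows the definition is open to incompatible readings, and the TBR reading has the difficulty in step 5.

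**There is a second route.** Fluorescence microscopy depends on ICG. As an additional route it can only add responders, and it needs neither the handheld OMI nor EM.

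**EM may contribute to reaching the lesion.** Sections 6.1.2 and 6.1.4.2 describe EM tracking in needle placement toward the target, which conflicts with 2.3.11. Independence from the devices is therefore firm for OMI and disputed for EM. Even where EM was used, reaching the lesion does not show that the displayed position was correct.

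**A failed exchange need not end the biopsy.** True, and the number of abandoned procedures is unknown. Such a patient stays in the denominator, as a responder if the lesion is reached.

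**A stronger inference the documents do not support.** A reader might conclude that the rate will be close to 100%, or that the trial will declare feasibility whatever the devices do. Section 9.4.1 has no threshold or decision rule, and no localization rate is given for this trial. The readily-biopsied criterion points to a high rate. The 45% visibility figure and the negative predictive values of 63% and 72% in 4.2 are reasons not to assume one.

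**Conclusion.** The point holds in this form: read literally, the 9.4.1 response does not depend on OMI output, does not show that the EM position was valid, and excludes uncompleted procedures that may be feasibility failures. It cannot by itself answer the primary objective. The items that could do so are in the plan under another name and are not linked to it.

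The size depends on assumed inputs. At L = 0.95 the literal count is 73 of 77 for any device performance, against 0 to 73 when device output is required. Eight abandoned procedures would move the rate by 10.4 percentage points (100 − 89.6). The conclusion does not depend on these values, because at any L the literal rate is uninformative about OMI. It rests on the bystander statements in 2.3.11, 4.2 and 6.1.2, and for EM it is subject to the conflict noted above. The kappa test and N = 77 stand. The definition should be changed, but the design is not invalidated.

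**What to change.** - **Outcome.** Replace the 9.4.1 response sentence with per-patient technical success: a usable in vivo OMI reading at both normal liver and target, so that a TBR can be calculated (item 3), and an EM fusion display of the biopsy location (item 4), with imaging confirmation of the region (item 2). State what makes a reading usable. State also that a display at odds with the confirmed region does not count.
- **Denominator.** Use all participants in whom study needle placement was started. Abandoned procedures and unusable readings count as failures. Section 5.5 already treats patients who become ineligible "prior to the biopsy, will be considered inevaluable"; they stay outside this denominator and are reported separately.
- **Reporting.** Give the proportion with an exact 95% CI as the feasibility result. If a pass mark is wanted, set it in advance; otherwise say the result is an estimate.
- **Links.** Stop calling the four-item check concordance in 4.1 and 9.4.3, and cross-refer it to this measure. Keep kappa as the agreement analysis.
- **Descriptive only.** Report localization by standard imaging, and fluorescence microscopy, separately.
- **Reconcile** 6.1.2 and 6.1.4.2 with 2.3.11 on whether EM is used to direct the needle.

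The cost is wording in 9.4.1, 4.1 and 9.4.3, plus case report form fields for unusable readings and abandoned procedures if these are not already recorded. The readings, displays and imaging are already planned, so no extra patients or procedures are needed. The downside is that the reported feasibility rate may be lower.
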